Preregistration on Clinicaltrials.gov

Project:

„Hypnosis Induction and Height Experience in VR - Control Group Comparison and Three Sessions“

Unique Protocol ID: 521/2019BO2

Description of the Hypotheses, Analyses and needed Sample Sizes

06.05.2024

1. Data collection. Have any data been collected for this study already?

No data has been collected for this study.

2. Hypothesis: What's the main question being asked or hypothesis being tested in this study?

- a. Do three sessions of VR therapy reduce the fear of heights in both groups?
 - i. We expect a decrease in fear of heights over the sessions.
 - ii. Fear of heights decreases over the three sessions, with the experimental group benefiting more from the sessions than the control group.
- b. The fear of heights increases less from after the last therapy session to the follow-up measurement after one week in the experimental group than in the control group.
- c. Does the anxiety experience curve change during the VR height confrontation over the three sessions in both groups?
 - i. We expect typical anxiety experience curves according to the habituation (linear increase in anxiety and quadratic decrease).
 - ii. We expect a decrease of the mean anxiety experience rating over the sessions.
 - iii. We expect that the anxiety experience curves rise less sharply with each session.
 - iv. We expect that the anxiety experience curves reach their turning point earlier with each session.
 - v. The experimental group has lower anxiety experience ratings across all sessions and rises (20 ascents during the height confrontation) compared to the control group.
- d. How does a person's suggestibility influence the perception and impact of the intervention?
 - i. More suggestible people show a greater reduction in anxiety over the three sessions than less suggestible people.
 - ii. The influence of suggestibility on the strength of reduction in anxiety over the three sessions is stronger in the experimental group than in the control group.
 - iii. Suggestibility and group affinity interact such that in the experimental group participants with higher suggestibility show a lower level of anxiety experience during the height confrontation than less suggestible participants, but in the control group higher suggestible participants exhibit greater anxiety experience during the height confrontation than less suggestible participants.

3. Analyses

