The analyses are carried out using linear mixed models. Each model is tested with the car::Anova() function (model comparison Typ II ANOVA) in R to determine the significance of the individual effects. The model equations are written down below and the abbreviations used for the effects are explained.

grp: experimental vs. control group (enters model equation as factor: experimental

group is reference group)

sugg: suggestibility (enters model equation as linear predictor)

a. HIQ ~ grp + sess + grp:sess + (1 | id)

sess: baseline vs. post first session vs. post second session vs. post third session (enters model equation as factor)

For hypothesis a(i) we investigate the significance of sess.

For hypothesis a(ii) we investigate the significance of grp:sess.

b. HIQ ~ grp + sugg + mtp + sugg:mtp + grp:sugg + grp:mtp + grp:sugg:mtp + (1 | id)

mtp: measurement time point, baseline vs. post third session (enters model equation as factor)

For hypothesis d(i) we investigate the significance of sugg:mtp.

For hypothesis d(ii) we investigate the significance of grp:sugg:mtp.

c. HIQ ~ grp + mtp + grp:mtp + (1 | id)

mtp: measurement time point, post third session vs. one-week follow-up (enters model equation as factor)

For hypothesis b we investigate the significance of grp:mtp.

d. fear ~ grp + sugg + sess + rise + rise^2 + grp:sugg + sess:rise + sess:rise^2 + (rise + rise^2 | id)

sess: first session vs. second session vs. third session (enters as linear predictor)

rise: 20 rises during each of the three sessions, these are entered as a centered variable into the model equation (centered at total mean)

For hypothesis c(i) we investigate the significance of rise and rise^2.

For hypothesis c(ii) we investigate the significance of sess.

For hypothesis c(iii) we investigate the significance of sess:rise.

For hypothesis c(iv) we investigate the significance of sess:rise^2.

For hypothesis c(v) we investigate the significance of grp.

For hypothesis d(iii) we investigate the significance of grp:sugg.

4. Sample Size

- a. Analysis a needs 56 participants to achieve a Power of 80% for the effects of interest.

- b. Analysis **b** needs 92 participants to achieve a Power of 80% for the effects of interest.
- c. Analysis **c** needs 60 participants to achieve a Power of 80% for the effects of interest.
- d. Analysis **d** needs 50 participants to achieve a Power of 80% for the effects of interest.

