In order to prevent insufficient Power due to drop-outs, about 10% more participants should be surveyed. A total of 100 participants should therefore be surveyed (50 per group). If it is not possible to survey 100 participants, some of the analyses mentioned above can also be carried out with fewer participants and (as indicated) still enough Power.

5. Exploratory Analyses

- a. Exploratory Relationships:
 - i. More suggestible people report a higher perceived presence in the VR environment than less suggestible people (in both groups).
 - 1. Correlation test (correlation between suggestibility and average experience of presence)
 - ii. More suggestible persons in the experimental group report a higher subjective trance depth than less suggestible persons in the experimental group.
 - 1. Correlation test (correlation between suggestibility and mean trance depth of the experimental group)
- b. Exploratory Analyses:
 - i. We expect a reduction in fear of heights after each session.
 - 1. $\text{HIQ} \sim \text{grp} + \text{mtp} + \text{grp:mtp} + (1 | \text{id})$ (for all sessions)
 - a. mtp: measurement time point, pre vs. post per session
 - ii. We expect that the experimental group shows a lower level of fear of heights in the one-week follow-up than in the pre-measurement of the second session (one-week follow-up after one session). (no investigation of the control group)
 - 1. $\text{HIQ} \sim \text{follow} + (1 | \text{id})$
 - a. follow: pre second session vs. one-week follow-up
 - iii. We also plan to look at how many subjects in the experimental group continue to report a fear of heights below the cut-off for inclusion in the study (HIQ Score > 29) after three months.
- c. Checks:
 - i. We expect no difference in suggestibility between the groups.
 - 1. $\text{sugg} \sim \text{grp} + (1 | \text{id})$
 - ii. We expect no influence of suggestibility on the initial extent of fear of heights
 - 1. $\text{HIQ} \sim \text{sugg} + (1 | \text{id})$
 - iii. We expect no difference in the initial extent of fear of heights between the two groups.
 - 1. $\text{HIQ} \sim \text{grp} + (1 | \text{id})$

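### Exploratory analysis 5a(i) expects a suggestibility-presence link in each group, but the one unrestricted correlation listed for it can only show an average link

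*SAP*

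**What the plan says.** Section 5 of the SAP, item a(i), states the expectation: "More suggestible people report a higher perceived presence in the VR environment than less suggestible people (in both groups"). Directly below it stands the only test given for it: "Correlation test (correlation between suggestibility and average experience of presence"). No group variable, subgroup, significance level, sidedness or decision rule is attached.

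The next item, a(ii), concerns trance depth and is limited to one group. Its test line says so: "Correlation test (correlation between suggestibility and mean trance depth of the experimental group").

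On numbers, section 4 sets the target: "A total of 100 participants should therefore be surveyed (50 per group"). The most demanding main analysis, b, "needs 92 participants to achieve a Power of 80% for the effects of interest". No sample size or power is given for a(i).

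**The concern.** The expectation is about two groups and the test is about one sample. If all participants enter a single correlation, the coefficient is a blend of the link under hypnosis and the link under control. A strong link in one group and none in the other can produce a significant positive result. Read against the stated expectation, that result would seem to confirm a link in both groups although one group has none.

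At stake is the correctness of one exploratory statement: whether suggestibility relates to presence in VR generally, or only under one of the two conditions.

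**Working it through.** The plan gives no figure for this test, so there is none to reproduce. The check is what a whole-sample correlation does when only one group carries a link.

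**Inputs from the SAP:** 100 participants, 50 per group (section 4). As a lower case, 92 analysable participants, the number required for analysis b, or 92 / 2 = 46 per group.

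**Assumptions, not in the SAP:** two-sided 5% level; bivariate normal data; equal variances in the two groups; no group difference in mean suggestibility or mean presence; true within-group correlations over a range.

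**Step 1, what the whole-sample correlation estimates.** With equal group sizes, equal variances and no mean shift, pooled r = (r1 + r2) / 2. For r1 = 0.4, 0.5 or 0.6 and r2 = 0, pooled r = 0.20, 0.25 or 0.30.

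**Step 2, how often it is significant.** By Fisher z, power ≈ Φ(atanh(r) × √(n − 3) − 1.96), with n = 100 and √97 = 9.849:

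- r = 0.20: 0.2027 × 9.849 = 1.997; Φ(0.037) = 51.5%
- r = 0.25: 0.2554 × 9.849 = 2.516; Φ(0.556) = 71%
- r = 0.30: 0.3095 × 9.849 = 3.048; Φ(1.088) = 86%

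A simulation with 40,000 replicates, counting significant results with positive r, agrees:

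| True r, one group / other | Whole-sample test, 50 per group | Whole-sample test, 46 per group | Significant in each group, 50 per group |
|---|---|---|---|
| 0.3 / 0 | 32% | 30% | 1.4% |
| 0.4 / 0 | 52% | 48% | 2.0% |
| 0.5 / 0 | 71% | 67% | 2.3% |
| 0.6 / 0 | 85% | 82% | 2.5% |

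Every row describes a link that is absent in one group.

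**Step 3, what a per-group requirement costs when the link is real in both.** Simulation, 50 per group:

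- r = 0.3 in each: each group alone is significant in about 57%, both together in 0.57 × 0.57 ≈ 33%; the whole-sample test in about 87%.
- r = 0.4 in each: each group alone in about 84%, both together in 0.84 × 0.84 ≈ 70%; the whole-sample test in about 99%.

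**Step 4, whether a positive sign in each group would be enough.** With r = 0.4 against 0, the first group's estimate is positive almost always: Φ(0.4236 × √47) = Φ(2.90) ≈ 99.8%. The other group's is positive half the time. The sign rule is therefore met in about 0.998 × 0.5 ≈ 50% of trials, hardly better than the whole-sample test's 52%.

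**The case against.** The strongest reply is that the SAP never says the correlation is taken over the whole sample. The mention of both groups may only mark scope: everyone is included, unlike a(ii). Section 2 uses similar wording for question a, and a(i) there is tested through the common session effect. Or the authors may intend one correlation per group. Under either reading the fault is loose wording rather than a mismatch. This stands as a qualification. The whole-sample reading is an inference, although the contrast with a(ii) makes it the natural one. The model for question a also carries a group-by-session term beside the common effect, whereas 5a(i) has nothing comparable. Each reading needs a clarifying line.

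Three stronger claims are tempting, and the document does not support them.

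- A reader might infer from hypothesis d(iii), which opens "Suggestibility and group affinity interact such that in the experimental group" and continues "but in the control group higher suggestible participants exhibit greater anxiety experience during the height confrontation than less suggestible participants", that the plan itself expects the presence link to differ by group. Hypotheses d(ii) and d(iii) concern anxiety. For presence the plan states the same direction in both groups.
- A reader might infer that links of opposite direction would be hidden, and so the test would fail the expectation. If the links are opposite, the expectation is false, and a null result does not wrongly reject it.
- A reader might infer that a group difference in mean presence would badly weaken the correlation. With an assumed shift of 0.8 SD, a common r of 0.3 becomes 0.3 / √(1 + 0.8² / 4) = 0.28, and power falls from 86% to 80%. That is small, and nothing in the SAP points to a shift of that size.

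It is also fair to say that the analysis is exploratory and that no rule obliges the authors to report a significant correlation as holding in both groups.

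**Conclusion.** The point holds in limited form. As naturally read, the test for 5a(i) addresses an average link and cannot establish the link in each group. If only one group carries it, the whole-sample test is significant in about 52% to 86% of trials for r from 0.4 to 0.6. The correlations, the 5% two-sided level and equal variances are assumptions. With 46 per group the range is 48% to 82%.

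The importance is low. No confirmatory hypothesis and none of the sample sizes in section 4 rest on this analysis. It is worth correcting because the correction is nearly free.

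**What to change.** Replace the test line under 5a(i) with a linear model, `presence ~ grp + sugg + grp:sugg`, one row per participant, using each person's average presence. Report three results: the suggestibility slope (or correlation) with its 95% confidence interval in each group, and the group-adjusted common slope from `presence ~ grp + sugg`.

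Add the decision rule. The link is stated for both groups only if the interval lies above zero in each. Otherwise the common slope is reported, and described as an average link. A positive sign in each group should not suffice, as step 4 shows.

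The cost is a line or two of wording and one extra model on data the study gathers anyway. Section 1 states that no data had been collected when the plan was written. The real downside is the loss of power in step 3, which is why the common slope should stay as the better-powered, more modest result. If the authors meant only a whole-sample link, the alternative is to reword the expectation to say so.
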